Appendix 3 Estimation of Treatment Effects for P&VFDs

Let Y be the number of P&VFDs for both survivors and non-survivors, let p be the probability of surviving, and say that for survivors (30-Y) has a negative binomial distribution (with for Y=0 consuming all values \geq 30).

$$P(Y = y) = \begin{cases} (1-p) + p * \sum_{k \ge 30} \frac{\Gamma(d^{-1} + k)}{\Gamma(d^{-1})k!} \left(\frac{\mu * d}{1 + \mu * d}\right)^k \left(\frac{1}{1 + \mu * d}\right)^{d^{-1}} & \text{for } y = 0 \\ p * \frac{\Gamma(d^{-1} + 30 - y)}{\Gamma(d^{-1})(30 - y)!} \left(\frac{\mu * d}{1 + \mu * d}\right)^{(30 - y)} \left(\frac{1}{1 + \mu * d}\right)^{d^{-1}} & \text{for } y > 0 \end{cases}$$

In the trial it is expected we have a mean of around 5-8 days on vasopressors and mechanical ventilation for those surviving.

Therefore, the probability of getting zero P&VFDs for those surviving

$$\sum_{k\geq 30} \frac{\Gamma(d^{-1}+k)}{\Gamma(d^{-1})k!} \left(\frac{\mu*d}{1+\mu*d}\right)^k \left(\frac{1}{1+\mu*d}\right)^{d^{-1}}$$
 is negligible (and can be omitted from the model),

For d=1/16

μ	5	6	7	8	9	10	11
$Var = \mu + \mu^2 d$	6.56	8.25	10.06	12	14.06	16.25	18.56
P(K≥30)	1.4*10-9	4.2*10-8	6*10 ⁻⁷	5*10 ⁻⁶	2.8*10-5	1.2*10-4	4*10 ⁻⁴

μ	12	13	14	15
$Var = \mu + \mu^2 d$	21	23.56	26.25	26.09
P(K≥30)	1.1*10-3	2.5*10 ⁻³	5.4*10 ⁻³	1*10-2

For $Y_1,...,Y_N$ we then get two likelihood functions,

$$L_1 = \prod_{y_i=0} (1-p)$$

and,

$$L_2 = \prod_{y_i > 0} p * \frac{\Gamma(d^{-1} + 30 - y)}{\Gamma(d^{-1})(30 - y)!} \left(\frac{\mu * d}{1 + \mu * d}\right)^{(30 - y)} \left(\frac{1}{1 + \mu * d}\right)^{d^{-1}}$$

Assuming that p is modeled as $\frac{e^{\beta_1}}{1+e^{\beta_1}}$, and μ as e^{β_2} , the two log-likelihoods then become,

$$l_1 = \sum_{y_i=0} \ln(\frac{1}{1+e^{\beta_1}}) = \sum_{y_i=0} -\ln(1+e^{\beta_1})$$

Page 54 of 80

and,

$$l_2 = \sum_{y_i > 0} \beta_1 - \ln(1 + e^{\beta_1}) + \ln(\Gamma(d^{-1} + 30 - y_i)) - \ln(\Gamma(d^{-1})) - \ln((30 - y_i)!) + (30 - y_i)(\beta_2 + \ln(1 + e^{\beta_2})) - d^{-1} * \ln(1 + e^{\beta_2})$$

Maximizing the full log-likelihood is thus maximizing $l_1 + l_2$.

And as can be clearly seen, the maximization of l_1 and l_2 with regards to β_1 does not depend on β_2 and vice-versa. Hence, β_1 and β_2 can be estimated separately from two independent models, i.e. a logistic regression for the probability of surviving, and a poisson regression (or negative binomial to allow for overdispersion) for the distribution of days on vasopressors and mechanical ventilation for those surviving.

In practice, and with the model adjusted for A, B and C, this means that the probability of surviving will be estimated from a logistic regression adjusted for A, B and C and treatment group. From each treatment group we can do an LSMEANS and get an 'overall' β_1 along with the standard error of β_1 .

For a given treatment group the mean probability of surviving is given as:

$$\frac{e^{\beta_1}}{1+e^{\beta_1}}$$

The distribution of days on vasopressors and mechanical ventilation (30- PVFD's) for those surviving will be estimated from a negative binomial regression (poisson with a potential overdispersion), also adjusted for A, B and C and treatment group. From each treatment group we can do an LSMEANS and get an 'overall' β_2 along with the standard error of β_2 .

For a given treatment group the mean PVFD's for survivors is given as:

$$(30 - e^{\beta_2})$$

The mean PVFD's for all subjects (survivors and non-survivors) is then given as:

$$\frac{e^{\beta_1}}{1 + e^{\beta_1}} * (30 - e^{\beta_2})$$

Let

$$f(\beta_1, \beta_2) = \frac{e^{\beta_1}}{1 + e^{\beta_1}} * (30 - e^{\beta_2})$$

Using the delta method we can calculate the variance of $f(\beta_1, \beta_2)$:

Page 55 of 80

$$f'(\beta_1, \beta_2) = \left(\left(30 - e^{\beta_2} \right) * \frac{e^{\beta_1}}{(1 + e^{\beta_1})^2} , \frac{e^{\beta_1}}{(1 + e^{\beta_1})} * \left(-e^{\beta_2} \right) \right)$$

Hence,

$$var[f(\beta_1,\beta_2)] = f'(\beta_1,\beta_2) \begin{pmatrix} \sigma_{\beta_1}^2 & 0 \\ 0 & \sigma_{\beta_2}^2 \end{pmatrix} f'(\beta_1,\beta_2)^t$$

$$= \left(\sigma_{\beta_{1}}^{2} * \left(30 - e^{\beta_{2}}\right) * \frac{e^{\beta_{1}}}{(1 + e^{\beta_{1}})^{2}} \quad \sigma_{\beta_{2}}^{2} * \frac{e^{\beta_{1}}}{(1 + e^{\beta_{1}})} * \left(-e^{\beta_{2}}\right)\right) \left(\frac{\left(30 - e^{\beta_{2}}\right) * \frac{e^{\beta_{1}}}{(1 + e^{\beta_{1}})^{2}}}{\frac{e^{\beta_{1}}}{(1 + e^{\beta_{1}})}} * \left(-e^{\beta_{2}}\right)\right)$$

$$= \sigma_{\beta_{1}}^{2} * \left(30 - e^{\beta_{2}}\right)^{2} * \left(\frac{e^{\beta_{1}}}{(1 + e^{\beta_{1}})^{2}}\right)^{2} + \sigma_{\beta_{2}}^{2} * \left(\frac{e^{\beta_{1}}}{(1 + e^{\beta_{1}})}\right)^{2} * e^{2\beta_{2}}$$

The 95% CI for the mean PVFD's then become

$$\frac{e^{\widehat{\beta_1}}}{1+e^{\widehat{\beta_1}}}*\left(30-e^{\widehat{\beta_2}}\right)\pm 1.96*\sqrt{var[f(\widehat{\beta_1},\widehat{\beta_2})]}$$

Let s indicate selepressin and p indicate placebo, the estimated treatment difference then becomes,

$$d = \frac{e^{\widehat{\beta_{1S}}}}{1 + e^{\widehat{\beta_{1S}}}} * \left(30 - e^{\widehat{\beta_{2S}}}\right) - \frac{e^{\widehat{\beta_{1p}}}}{1 + e^{\widehat{\beta_{1p}}}} * \left(30 - e^{\widehat{\beta_{2p}}}\right)$$

With 95% CI,

$$\frac{e^{\widehat{\beta_{1s}}}}{1 + e^{\widehat{\beta_{1s}}}} * \left(30 - e^{\widehat{\beta_{2s}}}\right) - \frac{e^{\widehat{\beta_{1p}}}}{1 + e^{\widehat{\beta_{1p}}}} * \left(30 - e^{\widehat{\beta_{2p}}}\right) \pm 1.96 * \sqrt{var[d]}$$

Where var[d] is derived again using the delta method as,

$$var[d(\beta_{1s}, \beta_{1p}, \beta_{2s}, \beta_{2p})] = d' \begin{pmatrix} \sigma_{\beta_{1s}}^2 & \sigma_{\beta_{1s}\beta_{1p}}^2 & 0 & 0\\ \sigma_{\beta_{1s}\beta_{1p}}^2 & \sigma_{\beta_{1p}}^2 & 0 & 0\\ 0 & 0 & \sigma_{\beta_{2s}}^2 & \sigma_{\beta_{2s}\beta_{2p}}^2\\ 0 & 0 & \sigma_{\beta_{2s}\beta_{2p}}^2 & \sigma_{\beta_{2s}}^2 \end{pmatrix} d'^t$$

With,

Page 56 of 80

$$d'(\beta_{1s}, \beta_{1p}, \beta_{2s}, \beta_{2p})^{t} = \begin{pmatrix} (30 - e^{\beta_{2s}}) * \frac{e^{\beta_{1s}}}{(1 + e^{\beta_{1s}})^{2}} \\ -(30 - e^{\beta_{2p}}) * \frac{e^{\beta_{1p}}}{(1 + e^{\beta_{1p}})^{2}} \\ -\frac{e^{\beta_{1s}}}{(1 + e^{\beta_{1s}})} * e^{\beta_{2s}} \\ \frac{e^{\beta_{1p}}}{(1 + e^{\beta_{1p}})} * e^{\beta_{2p}} \end{pmatrix}$$

In the above reasoning, it is assumed that P&VFDs can only take on integer values between 0 and 30. In practice, P&VFDs will be analysed with one decimal (with values in the range of 0, 0.1, ..., 29.9, 30.0) and hence the distribution of days on vasopressors and mechanical ventilation for those surviving will be estimated from a negative binomial regression model scaled up to 300 (transforming the P&VFDs from 0.0, 0.1, ..., 29.9, 30.0 to 0, 1, ..., 299, 300), and later scaled back to one decimal.

Let X = 10*Y (scaling Y from 0 to 300) and δ_1 and δ_2 the corresponding estimated parameters from the logistic regression and negative binomial regression models based on the modeling of X.

Transforming back to Y, the 95% CI for the mean P&VFDs (E(Y)) then become

$$\frac{e^{\widehat{\delta_1}}}{1+e^{\widehat{\delta_1}}} * \left(30 - \frac{e^{\widehat{\delta_2}}}{10}\right) \pm 1.96 * \sqrt{\frac{var[f(\widehat{\delta_1}, \widehat{\delta_2})]}{100}}$$

Again with s indicating selepressin and p indicating placebo, the estimated treatment difference then becomes,

$$\frac{e^{\delta_{1s}}}{1+e^{\delta_{1s}}} * \left(30 - \frac{e^{\delta_{2s}}}{10}\right) - \frac{e^{\delta_{1p}}}{1+e^{\delta_{1p}}} * \left(30 - \frac{e^{\delta_{2p}}}{10}\right)$$

With 95% CI,

$$\frac{e^{\widehat{\delta_{1s}}}}{1+e^{\widehat{\delta_{1s}}}}*\left(30-\frac{e^{\widehat{\delta_{2s}}}}{10}\right)-\frac{e^{\widehat{\delta_{1p}}}}{1+e^{\widehat{\delta_{1p}}}}*\left(30-\frac{e^{\widehat{\delta_{2p}}}}{10}\right)\pm1.96*\sqrt{\frac{var[f(\widehat{\delta_{1s}},\widehat{\delta_{2s}},\widehat{\delta_{1p}},\widehat{\delta_{2p}})]}{100}}$$

Page 57 of 80

Appendix 4 Estimation of Treatment Effects for Difference of Proportions in Incidence of RRT, and Difference in Number of New Organ Failures and Number of New Organ Dysfunctions

Estimation of Treatment Effects for Difference of Proportions in Incidence of RRT

Let Y be the incidence of RRT (and/or death).

Y can then be modelled using a logistic regression, adjusted for various factors and covariates.

In practice, and with the model adjusted for A, B and C, this means that the probability of RRT incidence will be estimated from a logistic regression (PROC GENMOD preferred over PROC LOGISTIC as estimates can be subtracted by ODS output) adjusted for A, B and C and treatment group. From each treatment group we can do an LSMEANS and get an 'overall'(adjusted) β along with the standard error of β and the covariance between the estimates from each treatment group. I.e. we get β_s , β_p , σ_{β_s} , σ_{β_n} , and $\sigma_{\beta_s\beta_n}^2$.

For a given treatment group the mean probability of RRT incidence is given as:

$$\frac{e^{\beta}}{1+e^{\beta}}$$

The difference in proportions of RRT incidence is then given as:

$$\frac{e^{\beta_s}}{1+e^{\beta_s}} - \frac{e^{\beta_p}}{1+e^{\beta_p}}$$

Using the delta method we can calculate the variance of $f(\beta_s, \beta_p)$:

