9.2.1 Primary Variable Analysis

The primary endpoint, P&VFDs, will be analyzed using a van Elteren test, stratified by need for ventilation (Yes/No), time from onset of shock (onset of any vasopressor) to start of treatment (< or \ge 6 hours), and norepinephrine/noradrenaline requirement at baseline (< or \ge 30 μ g/min).

The primary analysis will compare all patients on all selepressin arms from both parts of the trial (pooled together and treated as a single arm) to all patients on the placebo arm from both parts of the trial (see Appendix 7 for a discussion on treatment estimate bias).

The primary analysis will be a test of superiority using a two-sided 5% significance level test.

Treatment effects will be estimated assuming a negative binomial distribution (to allow for possible overdispersion in a Poisson distribution) for the quantity (30 minus P&VFDs) for survivors, and a binomial distribution to model the probability of surviving. Both models adjusted for need for ventilation (Yes/No), time from onset of shock to start of treatment (< or \geq 6 hours), and norepinephrine/noradrenaline requirement at baseline (< or \geq 30 µg/min) (see Appendix 3 for details). For completeness, the proportion of patients dying, and the P&VFDs for survivors will also be presented.

Page 26 of 80

Furthermore, P&VFDs will be tabulated by treatment arm (including pooled active treatment arms), and presented graphically by histograms and cumulative distributions functions.

The success (statistical/clinical significance) of the trial will be based upon the comparison of the analysis above (all patients on all selepressin arms from both parts of the trial (pooled together and treated as a single arm) compared to all patients on the placebo arm from both parts of the trial).

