9.3.2 Morbidity/Mortality

9.3.2.1 Intensive Care Unit (ICU)-free Days up to Day 30

ICU -free Days up to Day 30 will be defined and analyzed in a similar manner as the primary endpoint, with the van Elteren test stratified by need for ventilation (Yes/No), time from onset of shock to start of treatment (< or \ge 6 hours), and norepinephrine/noradrenaline requirement at baseline (< or \ge 30 µg/min) and baseline creatinine (< or \ge 150 µmol/L).

A sensitivity analysis will be performed where the definition of time spent in the ICU will include first admission to emergency department, as some patients will be enrolled and have first IMP treatment in the emergency department.

9.3.2.2 ICU Length of Stay up to Day 30

ICU length of stay is defined as the cumulative periods spent in ICU from start of IMP to 30 days after.

For patients withdrawn or dying while still in ICU up to Day 30, the duration will be based on the data available up until the time of withdrawal or death.

ICU length of stay will be analyzed between treatment groups using the permutation test specified in Section 9.3.1.3 stratified by the combination of time from onset of shock to start of treatment (< or \ge 6 hours), baseline creatinine (< or \ge 150 μ mol/L), norepinephrine/noradrenaline requirement at baseline (< or \ge 30 μ g/min) and need for ventilation (Yes/No).

A sensitivity analysis will be performed where the definition of time spent in the ICU will include first admission to emergency department, as some patients will be enrolled and have first IMP treatment in the emergency department.

9.3.2.3 All-cause Mortality (Defined as the Fraction of Patients That Have Died, Regardless of Cause, by the end of Day 30, Day 90, and Day 180)

Mortality will be analysed by a logistic regression model with the individual SOFA scores and age as covariates and treatment arm as factor. The 95% confidence interval for the difference in proportions between treatment groups will be constructed using the delta method as for incidence of RRT (section 9.3.1.8). There will be no imputations for mortality.

Non-inferiority will be claimed if the upper limit of the two-sided 95% CI of the adjusted difference in proportions is less than 30% of the estimated incidence of mortality in the placebo group. Superiority can be claimed (5) if the upper limit is less than 0.

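### Back-transformed LSMEANS are labelled population means and incidences, which they are not; the clearest effect is a mortality non-inferiority margin tighter than the SAP justifies

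*SAP*

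**What the plan says.** Section 9.2.1 estimates the P&VFD effect from two models, a logistic model for survival and a negative binomial model for 30 minus P&VFDs in survivors. "Both models adjusted for need for ventilation (Yes/No), time from onset of shock to start of treatment" and norepinephrine requirement.

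Appendix 3 takes one LSMEANS value per arm from each model. The inverse logit of the first is introduced by "For a given treatment group the mean probability of surviving is given as". The product expit(β1) × (30 − e^β2) is introduced by "The mean PVFD's for all subjects (survivors and non-survivors) is then given as". After rescaling to tenths of a day, the same quantity is called E(Y): "Transforming back to Y, the 95% CI for the mean P&VFDs (E(Y)) then become".

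Appendix 4 repeats the construction for RRT ("For a given treatment group the mean probability of RRT incidence is given as") and for counts of new organ failures and dysfunctions. Section 9.3.2.3 uses the RRT method for mortality, with the individual SOFA scores and age as covariates.

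These values feed two decision rules. In section 9.3.2.3 mortality is non-inferior if the upper confidence limit "is less than 30% of the estimated incidence of mortality in the placebo group". Section 9.3.1.8 has the same rule for RRT with 20%. Section 9.3.2.3 motivates the 30% by observed placebo mortality of 20–25%.

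**The concern.** LSMEANS averages the linear predictor: covariates are set at their means and, under the usual software default, factor levels get equal weight. The inverse logit or exponential of an average is not the average of the inverse logits or exponentials. The P&VFD product has a further problem. It multiplies two separate averages, so it loses any link across strata between survival and time on support.

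The quantity computed is therefore not the one named. The SAP plans with population figures throughout: 25% mortality, 18 P&VFDs, an effect of 1.5, and observed mortality of 20–25% behind the margin. The adjusted P&VFD means and the mortality and RRT incidences would be reported under labels they do not meet. The non-inferiority margins would be fractions of a placebo value different from the one that justified them.

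**Working it through.** **1. The plan's own figures are population (marginal) figures.**
- Appendix 8, placebo: 25% mortality and 24 P&VFDs in survivors give 0.75 × 24 = 18.0, as stated.
- Section 3.2: 1.5% lower mortality and 1.5 more days give 0.765 × 25.5 − 18 = 1.51 (stated 1.5). With 2% and 2 days, 0.77 × 26 − 18 = 2.02 (stated 2).
- Section 9.3.2.3 gives 2–3% as the tolerated excess; I read it as a difference. Solving x + 1.96·SE = 0.3·pP for 1800 patients, with 50–67% on active, gives 2.0–2.2 points at pP = 20% and 3.2–3.4 points at 25%. This matches only if pP is the population rate.

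**2. Mortality margin under the SAP formula.** The documents give no covariate effects, so assume a normal linear predictor with standard deviation σ. Choose the mean a so that the average of expit(a + σZ) equals the true rate. The SAP formula reports expit(a), and the margin is 0.3·expit(a).

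| True placebo mortality | σ | Reported | Margin | Margin from true rate |
|---|---|---|---|---|
| 25% | 0.5 | 23.9% | 7.2 | 7.5 |
| 25% | 0.7 | 22.9% | 6.9 | 7.5 |
| 25% | 1.0 | 21.2% | 6.4 | 7.5 |
| 25% | 1.5 | 17.8% | 5.3 | 7.5 |
| 20% | 0.5 | 18.9% | 5.7 | 6.0 |
| 20% | 1.0 | 16.1% | 4.8 | 6.0 |
| 20% | 1.5 | 12.8% | 3.8 | 6.0 |

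The values σ = 0.5, 1.0 and 1.5 correspond to an AUC of about 0.63, 0.74 and 0.82. The risk difference itself hardly moves: a true +2.0 points is reported as 1.9–2.2.

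**3. RRT or death, margin 0.2·expit(a), σ = 0.5 / 1.0 / 1.5.**
- True 30%: 5.8 / 5.3 / 4.7 points instead of 6.0.
- True 40%: 7.9 / 7.6 / 7.2 points instead of 8.0.
- True 50%: no change.

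The RRT model also has ventilation as a factor, so equal weighting could shift its value further in either direction.

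**4. Effect on the mortality non-inferiority decision.** I simulated 1000 trials per setting with N = 1800, 55% active, true placebo rate 25% and σ = 1.0.

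| True difference | SAP rule claims NI | Standardised rule claims NI |
|---|---|---|
| 0 | 86% | 96% |
| +3 points | 36% | 63% |
| +7.5 points | 0.6% | 3.9% |

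At +3 points the two rules disagree in 26% of trials. At σ = 0.5 the claims at +3 points are 50% and 58%.

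**5. P&VFD effect.** I used exact sums over the 8 cells of ventilation, time and norepinephrine. The marginal values were fixed at 75% survival and 6 days on support for placebo, and 76.5% and 4.5 days for selepressin. The true mean is then 18.0 and the true effect 1.51. Prevalences and coefficients (listed in that factor order) are assumed. Two equal-weight examples:
- Prevalences 0.65, 0.65, 0.30; logit-survival effects −0.7, −0.2, −0.7; log-days effects 1.0, 0.2, 0.4. Placebo: 0.7591 × (30 − 5.053) = 18.94. Selepressin: 0.7743 × (30 − 3.778) = 20.30. Effect 1.37.
- Prevalences 0.30 each; effects −0.3, −0.1, −0.4 and 0.4, 0.1, 0.2. Placebo: 0.7215 × (30 − 6.826) = 16.72. Selepressin: 0.7378 × (30 − 5.116) = 18.36. Effect 1.64.

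With observed-margin weights the same two cases give 1.46 and 1.50. Other assumed sets gave 1.45–1.76 and 1.15–1.50 with equal weights, and 1.51–1.52 and 1.41–1.51 with observed weights.

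**The case against.** The strongest reply is that little of consequence depends on this. Trial success rests on the van Elteren test, which uses no LSMEANS. RRT-free days and ICU-free days are tested the same way. Day-90 mortality enters the Hochberg procedure as a superiority test, whose limit is compared with 0. All of this stands.

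The SAP also describes the proportions as adjusted, and adjusted values need not equal raw rates. It tabulates raw P&VFDs, RRT and mortality by arm. That is fair, but the raw figures enter neither the effect estimate nor the margins, and calling a value adjusted does not make it the mean over all subjects or E(Y).

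Equal weighting is a software default that the SAP neither states nor excludes. The larger P&VFD shifts depend on it, so they are conditional. The premise that strata with low survival also have longer support is plausible, but the SAP does not state it.

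A reader might infer that the non-inferiority rules become too lenient. For evaluation at mean covariates and rates below 50%, the opposite holds: the margin shrinks, and claims at a true +7.5 points fall from 3.9% to 0.6%. A reader might also infer a large bias of known direction in the headline P&VFD effect. The documents do not support that, because the direction changes with prevalences the SAP does not give.

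**Conclusion.** The point holds as one of estimation and labelling, with a practical consequence for the non-inferiority margins. Appendices 3 and 4, and section 9.3.2.3 by reference, compute values at averaged covariates and name them population means and incidences.

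At an assumed true placebo mortality of 25%, the margin is 7.2–6.4 points for σ of 0.5–1.0, and 5.3 at σ = 1.5, against the 7.5 that a 30% margin on the observed rate implies. The rule is stricter than justified and loses power for a secondary claim. It does not create a false assurance of safety. The shift is small with weak covariates and nil near a 50% rate.

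For P&VFDs, the effect of 1.51 changes little with observed weights. With equal weights it can move either way, by an amount this SAP cannot fix. The evidence does not extend to the primary conclusion or to the superiority criteria. All sizes rest on the assumed covariate effects and prevalences shown above.

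**What to change.** Replace the back-transformed LSMEANS by standardisation, keeping the same models:
- For every patient in the analysis set (for RRT, every eligible patient), predict survival, survivor days, RRT or death under selepressin and under placebo.
- For P&VFDs, multiply predicted survival by 30 minus predicted days within each patient.
- Average over patients by treatment and take the difference, with a delta-method or bootstrap standard error.
- Use the standardised placebo incidence in the 0.3 and 0.2 margin rules.
- Treat the organ failure and dysfunction counts in Appendix 4 in the same way.

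If the sponsor prefers to keep LSMEANS, the minimum is to relabel the values as those of a reference patient, state the weighting of factor levels, and state which placebo rate sets each margin.

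The cost is SAP wording and modest programming. No new data or models are needed.

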Using the delta method we can calculate the variance of $f(\beta_s, \beta_p)$:

$$f'(\beta_s, \beta_p) = (e^{\beta_s}, -e^{\beta_p})$$

Hence,

$$var[f(\beta_{s}, \beta_{p})] = f'(\beta_{s}, \beta_{p}) \begin{pmatrix} \sigma_{\beta_{s}}^{2} & \sigma_{\beta_{s}\beta_{p}}^{2} \\ \sigma_{\beta_{s}\beta_{p}}^{2} & \sigma_{\beta_{p}}^{2} \end{pmatrix} f'(\beta_{s}, \beta_{p})^{t}$$

$$= (\sigma_{\beta_{s}}^{2} * e^{\beta_{s}} - \sigma_{\beta_{s}\beta_{p}}^{2} * e^{\beta_{p}}, \quad \sigma_{\beta_{s}\beta_{p}}^{2} * e^{\beta_{s}} - \sigma_{\beta_{p}}^{2} * e^{\beta_{p}}) \begin{pmatrix} e^{\beta_{s}} \\ -e^{\beta_{p}} \end{pmatrix}$$

$$= \sigma_{\beta_{s}}^{2} * e^{2\beta_{s}} + \sigma_{\beta_{p}}^{2} * e^{2\beta_{p}} - 2 * \sigma_{\beta_{s}\beta_{p}}^{2} * e^{\beta_{s}} * e^{\beta_{p}}$$

The 95% CI for the difference in the number of new organ dysfunctions then become

$$e^{\widehat{\beta}_{s}} - e^{\widehat{\beta}_{p}} \pm 1.96 * \sqrt{var[f(\widehat{\beta}_{s}, \widehat{\beta}_{p})]}$$

Appendix 5 Statistical Model for Adaptive Design Decisions

An Example Trial

Date: 20 Nov 2017 E-Statistical Analysis Plan-17877; Ver.9.0 Supersedes: Ver. 8.0 Page 59 of 80

This section presents the results of an example trial in order to illustrate how the design behaves. The selected scenario includes defining the probability distributions that describe how patients given placebo behave, and also defining the effects of all four selepressin dosing regimens. In the example trial we work with P&VFD data recorded to the nearest day instead of the nearest tenth of a day.

Figure 6 shows the data available at the first interim analysis, and the results of the statistical analyses performed using those data that are then used to make decisions. The leftmost of the three plots shows the raw data for each of the five arms, with mortality data in the legend and P&VFD data for survivors in the barplots. Red represents the placebo arm, and the shades of blue and black represent the active arms, with darker colors indicating larger maximum doses. The curves added to the plot are naïve density estimates that are not related to the statistical models used in the trial, scaled so that they have the same maximum. Active arm 2 has observed the highest mortality rate, while active arms 1 and 3 have seen tentative improvements compared to placebo. Active arm 3 has had the more surviving patients with small numbers of P&VFDs than the other arms. Active arm 4 is not yet allowed to accept patients. The middle plot displays estimates of mean P&VFDs (with fatalities scored as zero P&VFDs), together with 95% uncertainty intervals. The placebo arm is estimated to be the least effective, and uncertainties are smallest for the intermediate doses. The rightmost plot displays predictive probabilities and updated allocation probabilities. The circles show the allocation probabilities for the next 30 days: the probability for placebo remains at 1/3 for the duration of Part 1, and active arm 3 is assigned the lowest probability for any active arm. The rightmost plot also features squares showing the predictive probability that this trial would be successful if Part 1 were to terminate and Part 2 were to begin with each of the four arms as the chosen arm (It is too early to choose an arm: this can only happen when final data have been observed for at least 300 patients). If all four active arms had predictive probabilities less than 0.05 the trial would terminate for futility. Also, if the predictive probability were at least 90% that the final data set would show an observed increase in mortality of greater than 2%, regardless of which of the four active arms were selected, the trial would stop for futility for that reason, but these predictive probabilities are not shown in the figures.

Page 60 of 80

[figure not shown]

Figure 6: Data and interim analysis results at time of first interim analysis in an example trial

Moving ahead to the second interim analysis shown in Figure 7, when we have observed final data for 199 patients. Mortality has remained high for active arm 2. For survivors, the frequency of small numbers of P&VFDs is lowest for the placebo arm, but all three active arms have seen more patients with very large numbers of P&VFDs than has placebo. According to the rightmost plot, predictive probabilities for trial success are around 40% for all active arms. For the next 30 days, arm 3 will receive the highest allocation probability among the active arms, and since (not shown) the probability is at least 50% that arm 3's expected P&VFDs is higher than for arm 2, arm 4 becomes eligible for patient allocation to explore whether the apparent increasing trend in efficacy continues.

[figure not shown]

Figure 7: Data and analysis results for second interim analysis in example trial.

We skip ahead to the fourth interim analysis, shown in Figure 8, which is the first interim analysis after final data are available for at least 300 patients, so this is the first opportunity to choose a dose and move on to Part 2. The first data from arm 4 have come in, and arms 1, 3, and 4 are all achieving mortality rates no worse than placebo. The placebo arm continues to have the smallest probability of large numbers of P&VFDs among survivors. Since the predictive probability of trial

Page 61 of 80

success is largest for arm 3 and its value exceeds 90% (shown by the light green line), the trial elects to terminate Part 1 and proceed to Part 2 with arm 3. The allocation probabilities change to 50% each for placebo and active arm 3. Unless the trial stops earlier for futility, Part 2 will consist of 1430 patients since 370 are in the trial currently. The decision to select arm 3 occurs with only 11 patients allocated to arm 4, and with arm 4 looking promising thus far, but arm 3 has a high enough probability of a successful trial that the trial advances to Part 2.

[figure not shown]

Figure 8: Data and analysis results for fourth interim analysis in example trial

During this interim analysis, Part 1 terminates and the trial proceeds to Part 2 with active arm #3.

The first interim analysis of Part 2 takes place after 63 more patients are allocated to arm 3 or placebo. Final data continue to come in for the other active arms as well. Since data are relatively favourable for the placebo arm in this month, the predictive probability of a successful trial at 1800 patients drops to about 0.80, which is much larger than the 5% futility boundary for Part 2 of the trial.

[figure not shown]

Figure 9: First interim analysis during Part 2

Interim analyses continue every 30 days (frequency chosen for this example), with the only available decision being whether or not to stop for futility. The predictive probability of trial success never approaches the 5% value that would trigger a futility stop. The final data at the end of

Page 62 of 80

the trial are shown in Figure 9. Observed mortality was 2% lower for active arm 3 than for placebo, and the final analysis will be based on a smaller difference than this due to the inclusion of the data from other active arms. The simulation assumed true mortalities and expected P&VFD distributions for survivors are shown in the middle plot: the doses increase in effectiveness at both preventing mortality and increasing P&VFDs for survivors, with arms 3 and 4 each reducing mortality by 1.5% and increasing expected P&VFDs by 1.5 days for survivors. The rightmost plot shows the final p-value for the Wilcoxon test: the p-value for the comparison between patients given placebo and patients given any active arm is lower than 0.025, so this is a successful trial.

[figure not shown]

Figure 10: Results of final analysis. The trial is successful, with a p-value of 0.0068.

Statistical Model for Adaptive Design Decisions

A patient's outcome can be either death or a number of vasopressor and mechanical ventilator-free tenths of days between 0 and 300. Label d_i as the dose regimen assigned to patient i, and denote by s_i the stratum to which the patient belongs ($s_i \in \{0,1,...,7\}$). First, define the distribution of these potential outcomes for patients treated with placebo ($d_i = 0$). If the i'th patient dies, write $X_i = 1$, otherwise $X_i = 0$. So,

$$\Pr\{X_i = 1 | d_i = 0, s_i = 0\} = \Delta.$$

Intuitive parameterization of the P&VFD model

To motivate the strategy for modeling the distribution of the number of P&VFD given placebo and survival, we first define a version of the model that is more intuitive but less computationally convenient and is asymmetric with respect to the strata. The version actually recommended is defined below in the section "Symmetric, computational parameterization of the P&VFD model". The distribution can be modeled nonparametrically:

$$\Pr\{Y_i = k | d_i = 0, s_i = 0, X_i = 0\} = \pi_k, \text{ with } \sum_{j=0}^{300} \pi_j = 1.$$

Note that patients who die are modelled separately from patients who survive, but nevertheless accumulate zero P&VFD, although these patients are handled together in the final analysis. We model the treatment effect for a given dose d with two parts: the effect on mortality ϕ_d and the

Page 63 of 80

effect on P&VFD given survival, θ_d . The differences between the strata are modeled similarly to the effects of the different doses, with a stratum effect on mortality denoted by ψ_s and a stratum effect on P&VFD given survival denoted by ω_s . By definition $\psi_0 = \omega_0 = 0$. We model the effect on mortality, ϕ_d , on the log-odds scale:

$$\Pr\{X_i = 1 | d_i = d, s_i = s\} = \frac{\Delta}{\{\Delta + (1 - \Delta) \exp(\phi_d + \psi_s)\}'}$$

where we have defined the effect so that larger values of ϕ_d or ψ_s are beneficial (decrease mortality). We model the effects of the dose arm and the stratum on the number of P&VFDs for survivors using an exponential family whose sufficient statistic is the number of P&VFD:

$$\Pr\{Y_i = k | d_i = d, s_i = s, X_i = 0\} = \frac{\pi_k e^{k(\theta_d + \omega_s)}}{\sum_{j=0}^{300} \pi_j e^{j(\theta_d + \omega_s)}}.$$

In particular, given a dose arm, a sample of P&VFD, and a probability vector π , the maximum likelihood estimators of θ_d and ω_s set the expected values of P&VFD equal to their sample means.

In the final analysis, however, patients who died are treated in the same way as patients who survived but who had 0 P&VFD.

For the simpler statistical model with no consideration of stratum effects, the ψ_s and ω_s are omitted.

Symmetric, computational parameterization of the P&VFD model

The version of the statistical model we will actually use is as follows. There are still parameters $\pi_0, ..., \pi_{300}$, but they do not correspond directly to any stratum and do not have a clear interpretation of their own. Instead of assuming that $\psi_0 = \omega_0 = 0$, we use another choice of identifiability assumptions: $\sum_{s=1}^{8} \psi_s = 0$ and $\sum_{s=1}^{8} \omega_s = 0$. Now we have

$$\Pr\{Y_i = k | d_i = d, s_i = s, X_i = 0\} = \frac{\pi_k e^{k(\theta_d + \omega_s)}}{\sum_{j=0}^{300} \pi_j e^{j(\theta_d + \omega_s)}}$$

for all d and s, where we have defined the placebo parameter $\theta_0 = 0$. This parameterization facilitates the definition of prior distributions for the ψ_s and ω_s , and ensures that the results of the analysis do not depend on which stratum is identified with s = 0, etc. We assume hierarchical models on the stratum parameters, with $\psi_s \sim N(0, \tau_\psi^2)$ and $\omega_s \sim N(0, \tau_\omega^2)$ (conditionally on observing the identifiability assumptions), and with $\tau_\psi \sim \text{Uniform}(0,1)$ and $\tau_\omega \sim \text{Uniform}(0,1)$.

Page 64 of 80

Inverted-U dose-response models for the dose effects ϕ and θ .

Inverted U Dose-Response

[figure not shown]

Figure 11: Inverted-U dose-response model

The x-axis represents dose regimen (which is interpreted as maximum dose in the selepressin trial), and the y-axis represents the treatment effect. The model parameters ζ , γ , δ define theoretical special doses (e.g. γ is the smallest dose that gives maximal effect), while α denotes the maximum achievable treatment effect.

An inverted-U dose-response model is used for the effects on both mortality and P&VFD. This is a flexible family that allows for the possibilities that small doses have no effect at all (if those doses are smaller than ζ), and that large doses can start to become less effective than smaller doses (if those doses are larger than δ). Most importantly for this trial, the model allows all doses to be equally effective, since, for a given patient, any assigned maximum dose could be titrated to a similar delivered treatment. In the parameterization, shown in Figure 10, γ is the smallest dose that delivers maximal effect, δ is the largest dose that delivers maximal effect, ζ is the largest dose that delivers no effect, β is the rate at which performance degrades beyond dose δ , and α is the size of the largest effect ($\alpha \le 0$ is also allowed and there is a prior distribution for α which is symmetric about zero. To maintain an inverted U shape, β is constrained to be positive). Care must be taken to avoid important identifiability problems: in particular, it is insisted that the interval (γ, δ) contains at least one dose for which data can potentially be obtained, otherwise the largest treatment effect is not uniquely defined. However, γ can be smaller than any active dose, in which case the data contain no information about ζ , and δ can be larger than any active dose, in which case the data contain no information about β , but neither of these nonidentifiabilities are serious problems since they do not impact the ability to predict future data.

Page 65 of 80

In the case where the candidate doses are 1, 2, 3, and 4, a prior distribution is assumed in which

$$\delta - \gamma \sim \text{Uniform}(1,5),$$

 $\gamma | \delta \sim \text{Uniform}(0, \delta - 1), \text{ and}$
 $\zeta | \gamma \sim \text{Uniform}(0, \gamma).$

It is assumed that $\phi_d = IU(d|\alpha_1, \zeta_1, \gamma_1, \delta_1, \beta_1)$ and $\theta_d = IU(d|\alpha_2, \zeta_2, \gamma_2, \delta_2, \beta_2)$ for d = 1,2,3,4, where the inverted-U function is defined as

$$IU(d|\alpha, \zeta, \gamma, \delta, \beta) = \alpha \{ (1 - \left[1 - \frac{(d-\zeta)_+}{(\gamma-\zeta)}\right]_+ - \beta(d-\delta)_+ \}, \text{ where } x_+ = \max(x, 0).$$

There is no assumed relationship between the θ parameters and the ϕ parameters.

For a specific example, suppose $\alpha_1=0.2$, $\zeta_1=1.5$, $\gamma_1=2.5$, and $\delta_1=4$ (so that the value of β_1 is irrelevant for doses 1, 2, 3, and 4). Then $\phi_1=0$, $\phi_2=0.1$, $\phi_3=\phi_4=0.2$.

To complete the specification of the prior distribution, it is assumed that

$$\Delta \sim Beta\left(\frac{1}{3}, \frac{1}{3}\right), (\pi_0, \pi_1, ..., \pi_{300}) \sim Dirichlet\left(\frac{1}{30}, \frac{1}{30}, ..., \frac{1}{30}\right),$$
 $\alpha_1 \sim Uniform(-0.35, 0.35),$
 $\alpha_2 \sim Uniform(-0.01334, 0.01334),$
 $\beta_1 \sim Uniform(0, 10), \text{ and}$
 $\beta_2 \sim Uniform(0, 1).$

The limits for the α parameters are selected to be large but not completely absurd; e.g. $\alpha_1=0.35$ corresponds to a 5% benefit to a 20% mortality rate. Given P&VFD data, one can use a variable-at-a-time Metropolis-Hastings algorithm to sample from the posterior distribution of the unknown parameters $(\Delta, \pi_0, \pi_1, \dots, \pi_{300}, \alpha_1, \zeta_1, \gamma_1, \delta_1, \beta_1, \alpha_2, \zeta_2, \gamma_2, \delta_2, \beta_2)$. These samples can be used to estimate the predictive probability of a successful Part 2, the probability that each doses maximizes the expected number of P&VFDs, and the probability that dose regimen 3 provides a larger value of expected P&VFDs than does dose regimen 2.

The scale of α_2 depends on how P&VFDs are measured. Here they are recorded as integer numbers of tenths. If integer days are used instead, the prior range should be expanded by a factor of ten. The Dirichlet prior exponents we use also depend on how P&VFDs are measured: with integer days, we use exponents of 1/3 instead of 1/30. In either case the prior distribution corresponds to approximately ten equivalent observations.

Date: 20 Nov 2017 E-Statistical Analysis Plan-17877; Ver.9.0

Supersedes: Ver. 8.0 Page 66 of 80

Response-Adaptive Randomisation Probabilities

Beginning with the first interim analysis, allocation probabilities for the selepressin arms are adjusted based on the posterior distribution (the allocation probability for placebo remains fixed at 1/3 throughout Part 1). The allocation probability for active arm j is proportional to the posterior probability that arm j is one of the arms that maximizes the expected number of P&VFD (where the mortality probabilities are included in the calculations). Note that the inverted-U models allow for multiple arms to have exactly the same expected number of P&VFD.

